3.1 Study Population

3.1.1 Cohort One

Up to 14 subjects will be enrolled into Cohort 1. Subjects in Cohort 1 must have BCVA no better than 20/200 and no worse than Hand Motions (HM, i.e. the patient can distinguish horizontal from vertical hand motions at 1 foot). The first four subjects in Cohort 1 will receive an intravitreal injection of 0.5 x 10^6 hRPC (50 μ L volume) into the eye with the worst visual acuity; only one eye will be injected. The procedure does not require in-patient hospitalization and can be done under topical anesthesia. Subjects will be monitored closely following injection for 60 minutes prior to being released home on the day of treatment, based on intraocular pressure <30mm Hg and vital signs returned to pre-injection. Patients will be treated with ophthalmic corticosteroid eye drops to minimize any inflammation from injection for up to 14 days (including tapering schedule). There will be a minimum four week interval between the treatment of the first and second subjects in this cohort, with follow up at 1, 2, 3, 7, 14 and 21 days post-injection by the study investigator to confirm no serious injection related AEs have occurred for subject #1 prior to treatment of subject #2. Subsequent cohort 1 subjects at the same dose level will be spaced at least one week apart (subjects 2, 3 and 4), with follow up at 1, 2 and 3 days post-injection for each subject prior to treatment of the next subject at that dose level. All subjects will receive injection of cells into the eye with the poorest visual acuity. Following at least one week of safety observations for the last study subject at the lower dose level, safety and tolerability data will be reviewed by the DSMB. Assuming no unexpected safety issues and with DSMB recommendation, an additional 4 subjects will be enrolled in Cohort 1 and treated at the second dose level, 1.0 x 10⁶ hRPC. Treatment will be similar to the first four subjects, i.e. intravitreal injection under topical anesthesia with treatment of the first two subjects separated by at least 4 weeks and subsequent subjects in this cohort (subject 6, 7 and 8) spaced at least one week apart. Following at least one week of safety observation for the last Cohort 1 subject, safety and tolerability data will be reviewed by the DSMB prior to initiation of Cohort 2.

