3.2.2 Safety Endpoints

The primary goal of the study is to evaluate the safety and tolerability of jCell injection: The criteria that will be used to establish safety include:

- Slit-lamp findings, i.e., anterior chamber cell or flare; acute cataract development or progression in phakic patients, vitreous haze.
- Absence of tumor formation, overt immune rejection, decrease in BCVA attributable to treatment
- Absence of clinically significant, persistent increase in intraocular pressure (>10 mm Hg above baseline or IOP > 25 mm Hg), clinically significant epiretinal membrane, retinal detachment, neovascularization, or endophthalmitis
- No clinically significant adverse events attributable to investigational product (jCell) injection
- Patient comfort (no intolerable pain related to procedure)

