8.2.1 BCVA

BCVA will be tested at scheduled time points in both the treated and the contralateral eye. Visual acuity will be measured with the electronic visual acuity testing algorithm (E-ETDRS). E-ETDRS testing will be conducted using the electronic visual acuity tester (EVA). Based on estimates of 95% confidence intervals, a change in visual acuity of 0.2 logMAR (10 letters) from a baseline level is unlikely to be related to measurement variability using either the E-ETDRS or the S-ETDRS visual acuity testing protocol.

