8.2.2 Electroretinogram (ERG)

ERG examinations will be performed according to ISCEV standards and standardized among clinics to minimize difference between centers: briefly, patients are dark adapted for 30 min, electrodes attached under dim red illumination (dark room safe light). ERG responses will be recorded using single scotopically-balanced dim blue and red light flashes, and bright white flashes per detailed protocol. ERG at 6, 12 months are compared to pre-injection in terms of 1) a-wave amplitude, 2) b-wave amplitude, 3) time from flash onset to a wave trough and 4) time from flash onset to b-wave peak. In individual patients significantly faster deterioration of injected eye by ERG parameters and BCVA will halt further enrollment, although the latter measure is likely to be the more informative.

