9.1 Best Corrected Visual Acuity (BCVA)

For BCVA, summary statistics of the total number of letters correct (Letters correct=100-letters missed) will be generated at each time point for each cohort. Separate tables will be created for the Study Eye and the Non-Study Eye. In addition, change from baseline will also be summarized for each post baseline time point. For individual subjects who have number scores, the same formula for letters correct will be used to calculate each time point (letters correct = 100-letters missed). For subjects who do not have a number score e.g. counting fingers (CF), hand motions (HM) or no light perception)NLP), letters missed will be considered to be 100 and letters correct will therefore be zero. summarized (i) proportion of treated eyes with ≥ 5 , ≥ 10 and ≥ 15 letter

jCyte, Inc	Statistical Analysis Plan
Protocol No. JC-01	08Nov2017

improvements at any timepoint in the study same for untreated eyes at month 3,6,9 and 12 or Early Termination.

In addition, change in BCVA from baseline will be summarized for each dose level combining cohorts 1 and 2 at month 3,6,9 and 12 or early termination. Difference of mean change in BCVA between treated eye and non-treated eye from baseline will be summarized at month 3,6,9 and 12 or early termination. Furthermore, proportion of \geq 5, \geq 10 and \geq 15 letter improvements will be summarized for each dose level combining cohorts 1 and 2 at month 3,6,9 and 12 or early termination.

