n	n	n	n	n	n
Mean (SD)	$\mathbf{x}\mathbf{x}.\mathbf{x}(\mathbf{x}\mathbf{x}.\mathbf{x})$	xx.x (xx.x)	xx.x (xx.x)	xx.x(xx.x)	xx.x (xx.x)
Median	XX X	XX X	XX X	XX X	XX X
Min Max	XX XX	XX XX	XX XX	VV VV	XX XX
Ivini, ivian	лл, лл	лл, лл	лл, лл	ΔΛ, ΔΛ	лл, лл

^[1] Total includes both Cohorts 1 and 2.

^[2] Baseline is defined as the value obtained at the baseline visit. If the baseline value is missing, the baseline value will be the last non-missing value recorded prior to the first dose of study drug. path/t_program.sas date time

Programmer Note: Continue table for Visits: Day 3, Day 7, Day14, Day 21, Day 28, Month 2, Month 3, Month 4, Month 5, Month 6, Month 9, Month 12 or Early Term. Programmer Note: Table 14.2.1.2 will contain the same information for the Non-Study Eye
jCyte, Inc. Protocol: JC-01

	Cohort	1	Cohor	t 2	
	0.5 x 10 ⁶ hRPC (N=)		0.5 x 10 ⁶ hRPC (N=)		Total ^[1] (N=)
Proportion of Subjects with Specified increase in letters correct for any Post	(n=)	(n=)	(n=)	(n=)	(n=)
Baseline Assessment					
>=5 Letters Increase	n (%)	n (%)	n (%)	n (%)	n (%)
>=10 Letters Increase	n (%)	n (%)	n (%)	n (%)	n (%)
>=15 Letters Increase	n (%)	n (%)	n (%)	n (%)	n (%)
Proportion of Subjects with Specified increase in letters correct at Month 3	(n=)	(n=)	(n=)	(n=)	(n=)
>=5 Letters Increase	n (%)	n (%)	n (%)	n (%)	n (%)
>=10 Letters Increase	n (%)	n (%)	n (%)	n (%)	n (%)
>=15 Letters Increase	n (%)	n (%)	n (%)	n (%)	n (%)
Proportion of Subjects with Specified increase in letters correct at Month 6	(n=)	(n=)	(n=)	(n=)	(n=)
>=5 Letters Increase	n (%)	n (%)	n (%)	n (%)	n (%)
>=10 Letters Increase	n (%)	n (%)	n (%)	n (%)	n (%)
>=15 Letters Increase	n (%)	n (%)	n (%)	n (%)	n (%)
Proportion of Subjects with Specified increase in letters correct at Month 9	(n=)	(n=)	(n=)	(n=)	(n=)
>=5 Letters Increase	n (%)	n (%)	n (%)	n (%)	n (%)
>=10 Letters Increase	n (%)	n (%)	n (%)	n (%)	n (%)
>=15 Letters Increase	n (%)	n (%)	n (%)	n (%)	n (%)
Proportion of Subjects with Specified increase in letters correct at Month 12 or Eartly Termination	(n=)	(n=)	(n=)	(n=)	(n=)
>=5 Letters Increase	n (%)	n (%)	n (%)	n (%)	n (%)
>=10 Letters Increase	n (%)	n (%)	n (%)	n (%)	n (%)
>=15 Letters Increase	n (%)	n (%)	n (%)	n (%)	n (%)
ludes both Cohorts 1 and 2.					

^[1] Total in path\t_program.sas date time

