Programmer Note: Table 14.2.1.4 will contain the same information for the Non-Study Eye Programmer Note: Denominators used for percentage calculation to be based on number of results reported for that perticular time point.

Table 14.2.1.5 Best Corrected Visual Acuity (ETDRS): Study Eye vs Non-Study Eye Number of Letters correct ITT Population

	0.5 x	10 ⁶ hRPC	1.0 x	10 ⁶ hRPC	2.0 x	10 ⁶ hRPC	3.0x	10 ⁶ hRPC
	Study Eye (N=)	Non-Study Eye (N=)						
Baseline ^[1]								
n	n	n	n	n	n	n	n	n
Mean (SD)	xx.x (xx.x)	xx.x (xx.x)						
Median	xx.x	XX.X	xx.x	xx.x	xx.x	XX.X	xx.x	xx.x
Min, Max	xx, xx	XX, XX						
Month 3								
n	n	n	n	n	n	n	n	n
Mean (SD)	xx.x (xx.x)	xx.x (xx.x)						
Median	XX.X	XX.X	xx.x	XX.X	XX.X	XX.X	xx.x	XX.X
Min, Max	xx, xx	XX, XX						
Month 3 Change from Baseline								
n	n	n	n	n	n	n	n	n
Mean (SD)	xx.x (xx.x)	xx.x (xx.x)						
Median	xx.x	xx.x	xx.x	xx.x	xx.x	xx.x	xx.x	xx.x
Min, Max	xx, xx	XX, XX						
Difference between Study Eye Vs Non- Study Eye								
n		n		n		n		n
Mean (SD)		xx.x (xx.x)		xx.x (xx.x)		xx.x (xx.x)		xx.x (xx.x)
Median		XX.X		XX.X		XX.X		XX.X
Min, Max		xx, xx		xx, xx		xx, xx		XX, XX

^[1] Baseline is defined as the value obtained at the baseline visit. If the baseline value is missing, the baseline value will be the last non-missing value recorded prior to the first dose of study drug. path/t_program.sas date time

Programmer Note: Continue table for Visits: Month 3, Month 6, Month 9, Month 12 or Early Term.

jCyte, Inc. Protocol: JC-01

Table 14.2.1.6 Categorical Analysis of Best Corrected Visual Acuity (ETDRS): Study Eye vs Non-Study Eye Number of Letters correct ITT Population

	0.5 x 1	0 ⁶ hRPC	1.0 x 1	0 ⁶ hRPC	2.0 x 10	⁰ hRPC	3.0 x 10	0 ⁶ hRPC
	Study Eye (N=)	Non-Study Eye (N=)						
Proportion of Subjects with Specified increase in letters correct for any Post Baseline Assessment	(n=)	(n=)	(n=)	(n=)	(n=)	(n=)	(n=)	(n=)
>=5 Letters Increase	n (%)	n (%)						
>=10 Letters Increase	n (%)	n (%)						
>=15 Letters Increase	n (%)	n (%)						
Proportion of Subjects with Specified increase in letters correct at Month 3	(n=)	(n=)	(n=)	(n=)	(n=)	(n=)	(n=)	(n=)
>=5 Letters Increase	n (%)	n (%)						
>=10 Letters Increase	n (%)	n (%)						
>=15 Letters Increase	n (%)	n (%)						
Proportion of Subjects with Specified increase in letters correct at Month 6	(n=)	(n=)	(n=)	(n=)	(n=)	(n=)	(n=)	(n=)
>=5 Letters Increase	n (%)	n (%)						
>=10 Letters Increase	n (%)	n (%)						
>=15 Letters Increase	n (%)	n (%)						

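### SAP 9.1 scores every off-chart acuity as 0 letters, so an eye that falls from hand motions to no light perception is tabulated as unchanged in every BCVA summary table

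*SAP*

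**What the plan says.** SAP 9.1 defines letters correct as 100 minus letters missed and summarises the score and its change from baseline at each time point. For eyes without a number score it gives CF, HM and NLP as examples and rules that "letters missed will be considered to be 100 and letters correct will therefore be zero".

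Eyes at that floor are eligible. Protocol 3.1.1 states: "Subjects in Cohort 1 must have BCVA no better than 20/200 and no worse than Hand Motions". The eye with the poorer acuity is the one injected.

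The continuous BCVA shells (Tables 14.2.1.1, 14.2.1.2 and 14.2.1.5) give n, mean, SD, median, minimum and maximum. The categorical shells (Tables 14.2.1.3, 14.2.1.4 and 14.2.1.6) have rows only for gains of at least 5, 10 and 15 letters. Typical row headings are "Proportion of Subjects with Specified increase in letters correct at Month 3" and "Proportion of Subjects with Specified increase in letters correct for any Post Baseline Assessment". Tables 14.2.1.5 and 14.2.1.6 pool the cohorts, since "change in BCVA from baseline will be summarized for each dose level combining cohorts 1 and 2".

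SAP section 10 contains no BCVA analysis, and the Appendix B index lists no BCVA table under the safety heading 14.3. Yet Protocol 3.2.2 names among the criteria for establishing safety: "Absence of tumor formation, overt immune rejection, decrease in BCVA attributable to treatment".

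**The concern.** Safety is the primary objective, and loss of acuity in the injected eye is one of the protocol's own safety criteria. In the cohort with the worst vision, the scoring rule puts several clinically ordered states on one number. Deterioration among those states cannot appear in any BCVA summary, and neither can an improvement such as HM to CF.

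The coding is also uneven at the edge of the chart. An eye that goes from HM to 5 letters is counted as a gain of at least 5 letters. An eye that goes from 5 letters to HM has no count row.

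Protocol 8.2.2 shows that the protocol regards loss in single injected eyes as important: in individual patients, "significantly faster deterioration of injected eye by ERG parameters and BCVA will halt further enrollment". A final report that cannot count such losses from measured acuity leaves the reader to search listings and adverse event reports. The floor can also distort the study-eye minus fellow-eye difference in Table 14.2.1.5, in either direction.

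**Working it through.** **Inputs.** Scoring rule: SAP 9.1. Planned cells per cohort: 4, 4, 3 and 3 subjects across the four dose levels (Protocol 3.1.1 and 3.1.2). Pooled dose cells: 8, 8, 6 and 6. Total: 2 × (4 + 4 + 3 + 3) = 28. Benchmark, Protocol 8.2.1: "a change in visual acuity of 0.2 logMAR (10 letters) from a baseline level is unlikely to be related to measurement variability".

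**The plan's own figure.** Letters correct = 100 − letters missed. With 100 missed, 100 − 100 = 0, as SAP 9.1 states.

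**Off-chart moves.** Change = later score − baseline score.
- HM to NLP: 0 − 0 = 0.
- CF to NLP, CF to HM, HM to CF: also 0.

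If one eye goes from HM to NLP and the others are stable, the true share worsened is 1/3 = 33.3%, 1/4 = 25.0%, 1/6 = 16.7% or 1/8 = 12.5%, for n = 3, 4, 6 or 8. Tabulated mean, median and minimum change are 0 in each case. They are still all 0 if all 4 eyes of a cell go from HM to NLP.

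**The cap.** A fall from x letters to off-chart is recorded as 0 − x = −x. With the other eyes stable, the cell mean is −x/n:

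| Baseline x | Recorded change | Mean, n = 3 / 4 / 6 / 8 | Loss thresholds met |
|---|---|---|---|
| 4 | −4 | −1.33 / −1.00 / −0.67 / −0.50 | none |
| 9 | −9 | −3.00 / −2.25 / −1.50 / −1.13 | ≥5 |
| 14 | −14 | −4.67 / −3.50 / −2.33 / −1.75 | ≥5, ≥10 |

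A baseline of 15 letters is the lowest that can record a 15-letter loss. Below 10 letters the benchmark change can be recorded only as a gain.

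**Losses between two number scores.** An illustrative cell of 4 with changes −15, +5, +5, +5 has mean (−15 + 15)/4 = 0 and SD 10.0. The categorical table shows 3/4 gaining at least 5 letters and has no row for the loss. The minimum of −15 does show it. How far such losses can be read from the planned summaries depends on the cell:
- n = 3: minimum, median and maximum are the three values, so nothing is lost.
- n = 4: twice the median gives the sum of the two middle values, and the SD then fixes their difference, apart from rounding.
- n = 6: not determined. The sets (−15, −10, −5, −2, 1, 5) and (−15, −9, −7, 0, 0, 5) both have sum −26 (mean −4.33), sum of squares 380 (SD = √[(380 − 26²/6)/5] = 7.31), median −3.5, minimum −15 and maximum 5. The first has two losses of at least 10 letters, the second has one. The pooled table alone therefore cannot give the count. A reader would have to rebuild it from the two cohort cells.
- Any visit: per-visit summaries do not link one eye across visits, so a count of eyes with a loss at any visit cannot be recovered, although the gain tables have that row.

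**Eyes that could start at 0.** None to all 14 in Cohort 1, so 0/28 to 14/28, or 0% to 50%. The upper limit takes the Cohort 2 acuity range to apply to the injected eye.

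**The case against.** The strongest reply has five parts.

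- **Numeric losses are not hidden.** This stands for cells of 3 and, nearly so, for cells of 4. A reader might infer that the plan conceals all acuity loss. It does not: the gap is in off-chart moves, any-visit counts and the pooled table.
- **Adverse events cover it.** The treatment-emergent tables count reported losses, Table 14.3.1.3 covers related ones, and Protocol 9.1 treats significant or unexpected worsening of RP as an adverse event. This is also the route that addresses attribution, which letter counts cannot. It does not replace measured acuity. It depends on reporting, has no letter threshold, and leaves out progression judged to be expected.
- **Subject listings show it.** Listing 16.2.6.1 has an acuity Measurement column per eye and visit, and the physical examination listing records changes in vision or light perception. With at most 28 subjects this helps. But these are not summaries, and the BCVA shell shows only a fraction-style placeholder, so it does not establish that the categories are displayed.
- **The cap belongs to the instrument.** Any letter score stops at 0, and Protocol 3.2.1 concedes that BCVA is a poor measure in very low vision. True, but that is a reason to show the categories beside the letters.
- **The study is exploratory and BCVA is filed under efficacy.** No test is planned and none is asked for here. Acuity loss remains a stated safety criterion.

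Two further inferences are not supported. The enrollment halt in Protocol 8.2.2 is not run from SAP tables, so the scoring rule does not disable it. Nor do the documents show that results are biased in favour of treatment, because the floor hides off-chart gains as well as losses.

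**Conclusion.** The point holds. It follows from the scoring rule by arithmetic and needs no assumption about the data: moves among off-chart categories are tabulated as 0 in every BCVA summary, and a loss to off-chart cannot exceed the baseline letters. The lack of loss rows is secondary, because much of that information can be rebuilt in the smallest cells.

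The practical size is unknown. The documents do not say how many eyes start at or fall to the floor. The 12.5% to 33.3% figures illustrate one worsening eye with all others stable and are not estimates. No alpha, power or sample-size figure is affected. The plan should be changed because a named safety criterion otherwise has no summary of measured values that works in the worst-seeing eyes.

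**What to change.** **Main change.**
- Add one baseline-by-visit shift table on the ordered scale numeric > CF > HM > LP (light perception) > NLP, for study and fellow eyes, presented with the safety tables.
- First confirm that the off-chart categories are held in the Measurement field behind Listing 16.2.6.1. SAP 9.1 does not name LP, so check that category specifically.
- In Tables 14.2.1.1, 14.2.1.2 and 14.2.1.5, footnote the number of eyes scored 0 at baseline and at each visit.

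**Secondary change.** In Tables 14.2.1.3, 14.2.1.4 and 14.2.1.6, add losses of at least 5, 10 and 15 letters beside the gain rows, noting how many eyes had a baseline too low to record each loss. These rows will not detect HM to NLP, whose letter change stays 0, and they do not show attribution to treatment. The 5-letter row mirrors the gain row but lies below the protocol's 10-letter benchmark.

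**Cost.** A sentence in SAP 9.1, one new shell, added rows in three shells and a footnote in three. No new visits or tests are needed. If the categories are not in the database, the shift table cannot be built until they are recovered from source. Cells of 3 or 4 are very small, so the counts are descriptive only.

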9.2 Electroretinogram (ERG)

Electroretinogram (ERG) results will be summarized using both continuous and categorical methods. Descriptive statistics by eye (Study, Non-Study) of A-wave Amplitude, B-wave Amplitude, Time from Flash Onset to A-wave Trough and Time from Flash Onset B-wave peak endpoints will be calculated for each time point and condition specified in Section 8.1. Summaries of change from baseline will be presented in a similar fashion. In addition, count and percentages of overall ERG assessments of the following categories will be shown for each time point, eye (Study, Non-Study) and condition specified in Section 8.1:

- Normal
- Abnormal, Not Clinically Significant (NCS)
- Abnormal, Clinically Significant (CS)

9.3 Visual Field Examination

From the visual field examination, whether the results are Normal, Abnormal NCS and Abnormal CS will be summarized with counts and percentages at each time point for both study eye and non- study eye.

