3.2 Endpoints

3.2.1 Efficacy Endpoints

The response to jCell injection will be assessed based on the following:

- Change in BCVA at scheduled time points compared to baseline as well as contralateral eye. Acuity testing will be standardized using E-ETDRS.
- Changes in ellipsoid zone (EZ) band width at specified time points based on Spectral Domain Optical Coherence Tomography (OCT) compared to baseline as well as contralateral eye.
- Changes in electroretinogram (ERG) physiologic analysis compared to baseline as well as contralateral eye.
- Visual field sensitivity at scheduled time points post-treatment, using Goldmann visual field area and Humphrey 10-2, in subjects with adequate fixation to allow reliable testing.

In addition to the assessments listed above, a number of visual assessments that may be more appropriate for low vision subjects have been recommended by low vision experts. While BCVA is the gold standard for vision assessment, it is clear that this test is not particularly CONFIDENTIAL 16 of 41

relevant or accurate for subjects with very poor vision (legally blind). As there is little experience with our treatment approach, and subjects with very advanced vision loss are included in Cohort 1, it is planned to try some non-invasive assessments in subgroups of subjects, dependent upon the subjects' visual range and capabilities. These assessments include but are not limited to trial frame refraction, testing for contrast sensitivity (examples include Pelli-Robson Contrast Sensitivity Chart, Mars Letter Contrast Sensitivity Test, low luminance testing and mixed contrast eye charts); testing for color vision changes (e.g. D15 large caps, pseudoisochromatic plates), FrACT, California Central Visual Field Test, Tangent Screen Perimetry, ADL questionnaire (e.g. VFQ25, activity inventory, Low Vision Visual Functional Questionnaire [LF-VFQ], Function Independence Measures [FIM], Prosthetic Low Vision Rehabilitation [PVoVR]) and testing for changes in reading ability (e.g. Continuous Text Reading, MN Read). The goal of exploring some or all of these assessments is to develop a qualified, quantitative tool or set of tools for assessing post-treatment changes.

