8.1.5 Ophthalmic AEs

Procedures will be performed at scheduled intervals to specifically assess eye AEs that may not be detected by usual AE reporting. Please refer to the study procedure manual for details of all ophthalmologic assessment procedures.

Slit lamp and fundus exam - The binocular slit-lamp examination provides a stereoscopic magnified view of the eye structures in detail, enabling anatomical diagnoses to be made for a variety of eye conditions. This assessment will include detection of anterior chamber cell or flare; acute cataract development or progression in phakic patients, or vitreous haze. Fundus exam allows for inspection of the retina, the cellular graft, and detection of retinal detachment.

B-scan – B-scan is a test that uses high-frequency sound waves to get measurements and produce detailed images of the eye. This test may provide information regarding the location of the injected cells and the size of the cell clusters at different time points during the study.

IOP - Intraocular pressure is measured with a tonometer as part of a comprehensive eye examination. Measured values of intraocular pressure are influenced by corneal thickness and rigidity

Spectral Domain Optical Coherence Tomography (OCT) - A clinical OCT machine will be used for data collection; the same machine should be used for any given patient at each time point. OCT tests, including assessment of the ellipsoid zone (EZ), will be analyzed to help define retinal anatomy, and will enable monitoring for ocular inflammation after treatment as manifest by cystoid macular edema or epiretinal membrane formation or progression.

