8.2.3 Visual Field Testing

Visual field sensitivity will be assessed at scheduled time points post-treatment, using Goldmann visual field area and Humphrey 10-2, in subjects with adequate fixation to allow reliable testing.

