8.1 Efficacy Variables

The response to jCell injection will be assessed based on the following:

- Best Corrected Visual Acuity (BCVA): BCVA will be measured with the electronic visual acuity testing algorithm (E-ETDRS). For each time point assessed, the total number of letter missed using E-ETDRS will be recorded for each eye and recorded on the Best Corrected Visual Acuity (BCVA) case report form.
- Electroretinogram (ERG): For each eye, A-wave Amplitude, B-wave Amplitude, Time from Flash Onset to A-wave Trough and Time from Flash Onset B-wave peak will be measured under the following conditions:
 - Dark adapted 0.01 ERG (rod response)
 - Dark adapted 3.0 ERG (rod-cone response)
 - Light adapted 3.0 ERG (single flash cone response)
 - Light adapted 3.0 flicker ERG

In addition, an overall assessment of Normal or Abnormal will be recorded for each condition. For those assessments of Abnormal, whether the assessment was Clinically Significant will also be reported. If Clinically Significant value is not reported in the follow-up visit, then the value will be imputed based on the value of previous visit, consistent with CRF completion guidelines. For example, if abnormal change from previous visit is "NO" then imputed value will be value from the previous visit.

• Optical Coherence Tomography (OCT): for assessment of OCT, the central subfield thickness reported on the Optical Coherence Tomography case report

jCyte, Inc	Statistical Analysis Plan
Protocol No. JC-01	08Nov2017

form will be used. Also information recorded at each visit as to whether Cystoid macular edema (CME) was present and if so, did it involve the foveal center will also be considered.

- Fluorescein Angiography: information regarding active leakage (Yes/No) and ischemia (Yes/No) will be collected for each eye for each Fluorescein Angiography performed.
- Autofluorescence: an overall assessment of Normal or Abnormal will be recorded for each eye for each fundus auto fluorescence imaging performed. For those assessments of Abnormal, whether the assessment was Clinically Significant will also be reported. If Clinically Significant value is not reported in the follow-up visit, then the value will be imputed based on the value of previous visit, consistent with CRF completion guidelines. For example, if abnormal change from previous visit is "NO" then imputed value will be value from the previous visit.

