- Visual Field Test: an overall assessment of Normal or Abnormal will be recorded for each eye for each visual field examination performed. For those assessments of Abnormal, whether the assessment was Clinically Significant will also be reported. In addition, information regarding Mean Deviation, Fixation Loss, False Positives and False Negatives will also be recorded. If Clinically Significant value is not reported in the follow-up visit, then the value will be imputed based on the value of previous visit, consistent with CRF completion guidelines. For example, if abnormal change from previous visit is "NO" then imputed value will be value from the previous visit.

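### The SAP plans no analysis of two protocol efficacy measures, EZ band width and Goldmann field area, and tabulates visual field and OCT only as grades and edema counts

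*SAP*

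**What the plan says.** Protocol 3.2.1 gives four efficacy bullets. The OCT bullet reads "Changes in ellipsoid zone (EZ) band width at specified time points based on Spectral Domain Optical Coherence Tomography (OCT) compared to baseline", and it adds the contralateral eye as a second comparison. The field bullet reads "Visual field sensitivity at scheduled time points post-treatment, using Goldmann visual field area and Humphrey 10-2", limited to subjects who fixate well enough for reliable testing. Protocol 8.2.3 repeats both field methods: "Visual field sensitivity will be assessed at scheduled time points post-treatment, using Goldmann visual field area and Humphrey 10-2". Protocol 8.1.5, under ophthalmic adverse events, says "OCT tests, including assessment of the ellipsoid zone (EZ), will be analyzed to help define retinal anatomy", without mentioning band width.

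SAP 8.1 opens its list with the same lead sentence as Protocol 3.2.1, "The response to jCell injection will be assessed based on the following", but the list differs. For OCT it says "for assessment of OCT, the central subfield thickness reported on the Optical Coherence Tomography case report" form will be used, together with the presence of cystoid macular edema and foveal involvement. For the field it gives an overall Normal or Abnormal grade and adds that "information regarding Mean Deviation, Fixation Loss, False Positives and False Negatives will also be recorded".

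SAP 9 promises summary statistics, by cohort and dose level, for all efficacy variables. The specific sections are narrower. SAP 9.3 and Table 14.2.3 plan that "whether the results are Normal, Abnormal NCS and Abnormal CS will be summarized with counts and percentages at each time point". SAP 10.7.6 and Tables 14.3.4.12.1 and 14.3.4.12.2 count eyes with edema and, among those, foveal involvement.

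**The concern.** The secondary objective is to monitor ocular function over 12 months. If the SAP is followed as written, two measures that the protocol names go unreported, and the OCT measure that the SAP names for itself is never summarised.

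The SAP's disclosure rule does not close the gap. SAP 1 commits to documenting deviations from the SAP in the study report. EZ width and Goldmann area are not in the SAP, so leaving them out is not such a deviation.

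The field scale is also coarse. Protocol 1.1.1 says that rod loss in this disease affects peripheral vision, so few Normal grades can be expected at baseline. Abnormal CS is the worst of the three grades, so an eye that starts there can only stay or improve in Table 14.2.3, even if its Mean Deviation falls. Edema counts are useful for safety but measure neither EZ width nor thickness.

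These measures matter more because Protocol 3.2.1 itself doubts how informative BCVA is in very poor vision, and SAP 9.1 scores eyes without a number score as zero letters.

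**Working it through.** The plan states no figure to reproduce, and the sample size has no formal basis (SAP 4). The check is a trace of each measure through the documents.

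| Measure | Protocol | SAP 8.1 variable | SAP summary table | SAP listing |
|---|---|---|---|---|
| EZ band width | 3.2.1: change from baseline, and against the fellow eye | none | none | none |
| Goldmann area | 3.2.1 and 8.2.3 | none | none | technology name only, no area column |
| Humphrey 10-2 Mean Deviation | method in 3.2.1 and 8.2.3; Mean Deviation itself not named | recorded | none (grade only, Table 14.2.3) | 16.2.6.6 |
| Central subfield thickness | not an endpoint | named | none (edema counts only) | 16.2.6.3 |

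In the SAP, EZ otherwise appears only in the abbreviation list. The SAP does not say which technology yields Mean Deviation; I take it to be Humphrey 10-2.

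**Change summaries planned.** The four bullets of Protocol 3.2.1 name 5 measures: BCVA, EZ width, ERG, Goldmann area and Humphrey 10-2. The SAP text plans continuous change summaries for 2 of them, BCVA (9.1) and ERG (9.2). Across the whole SAP, change from baseline is stated for five groups: BCVA, ERG, laboratory values (10.3), vital signs (10.4) and IOP (10.7.2). It is not stated for field or OCT. The general sentence in SAP 9 can be read to cover levels of Mean Deviation and thickness. It does not mention change, and no table shell delivers either.

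**Recorded change series without a planned summary, per cohort and dose cell.**
- Mean Deviation: 2 visits (Months 6 and 12) x 2 eyes = 4.
- Thickness: 4 visits (Day 28, Months 3, 6 and 12) x 2 eyes = 8, or 5 x 2 = 10 if Month 9 counts.
- Total: 4 + 8 = 12, or 4 + 10 = 14.

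**Cells.** 2 cohorts x 4 dose levels = 8. The two lower dose levels hold 2 x (4 + 4) = 16 subjects. The two higher levels, which are optional, add at most 2 x (3 + 3) = 12, for a maximum of 28. Each cell therefore holds 4 or 3 subjects if filled.

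**How little such a cell can show.** The SAP plans no intervals. For scale, the 95% half-width of a mean change is t(0.975, n-1)/sqrt(n) in SD units: 4.303/1.732 = 2.48 SD for n = 3, and 3.182/2 = 1.59 SD for n = 4. Field cells will often be smaller because of the fixation limit.

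**The case against.** The strongest reply is that change tables for Mean Deviation and thickness are a preference. Thickness is not a protocol endpoint. The field bullet, unlike those for BCVA, EZ width and ERG, names neither change nor a fellow-eye comparison. A reader might infer that the protocol owes a change analysis for all five measures; its wording does not say so, and 8 to 10 of the 12 to 14 series counted above concern thickness. That limit stands. Against it, Protocol 10.2 makes the injected eye's own baseline its control, which is a change-from-baseline comparison. (SAP 9 names the non-injected eye's baseline instead, a difference that also needs reconciling.) The SAP also chose thickness as a variable and promises summary statistics for every efficacy variable.

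Second, the three-grade field summary is defensible. The field listing allows Goldmann, Humphrey 10-2 or another technology, and a grade works across all of them. The edema table fits the purpose that Protocol 8.1.5 gives for OCT. Both are reasons to keep these tables, not reasons to omit the others.

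Third, the listings preserve Mean Deviation, thickness and a change flag for each subject, so nothing recorded is lost. That is correct, but a listing is not a summary, and SAP 5 requires analyses not defined before database lock to be labelled post hoc. In a study without hypothesis tests that label costs little.

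Fourth, a reader might infer that EZ width and Goldmann area were measured and then left out. The documents do not support that. SAP 5 says that individual CRF data go into listings, and the layouts have no column for either measure. This suggests, without proving it, that neither was captured. The CRF is not among the documents.

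**Conclusion.** The point holds as a gap in planned descriptive reporting. EZ band width and Goldmann area are protocol efficacy measures for which the supplied SAP plans nothing and gives no reason. Mean Deviation and central subfield thickness are recorded but reach no summary table, despite the general promise in SAP 9.

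Its size is modest. The measures are secondary, the study is exploratory, and no error rate or sample size depends on them. A reader might go further and conclude that the field table will hide worsening in most eyes. The ceiling is real for any eye graded Abnormal CS at baseline, but the share of such eyes is not stated, so no count can be given.

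The conclusion rests on the SAP text supplied. Part of its front matter was not available, but the method sections and table shells relied on here were. ERG is not part of the point, because SAP 9.2 already plans continuous and change summaries for it.

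**What to change.** Before database lock, or labelled post hoc if lock has passed:

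1. Add descriptive level and change-from-baseline tables by cohort, dose level and eye, in the layout of Tables 14.2.1.1 and 14.2.1.2. Cover Humphrey 10-2 Mean Deviation at Months 6 and 12, restricted to eyes tested with the same technology at baseline and at that visit, and central subfield thickness at the scheduled OCT visits.
2. First reconcile the Month 9 OCT visit. It is marked in Protocol Table 2 and in the OCT table shell, but is absent from Protocol 7.5.12 and from Listing 16.2.6.3.
3. If EZ band width and Goldmann area were captured, report them, with the fellow-eye comparison that the protocol states for EZ width. If not, say so in the SAP and justify the departure from Protocol 3.2.1.
4. Keep the categorical field table and the edema tables.

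The cost is short text in SAP 8.1, 9.3 and 10.7.6 and four shells (2 measures x 2 eyes), plus shells for EZ width and Goldmann area if values exist. Mean Deviation and thickness are already in the listings, so item 1 needs no new data. The drawback is cells of 3 or 4 subjects, or fewer for the field: the tables can describe the course of these measures but cannot establish an effect.
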